# Measures during baseline

**Child Maltreatment Risk:** We will collect official records of child maltreatment from the Department of Children and Families. We will also collect logs of child maltreatment risk behaviors (harsh discipline and hostility toward the child) as reported on time line follow-back calendars during treatment. Parents will report on their harsh/hostile behavior on the Conflict Tactics Scale-Parent Child Version. These will be used to inform masked coder ratings on the Family Socialization Interview (FSI-R; our primary outcome measure). The FSI-R assesses severity of child maltreatment risk based on a compilation of data from self- report, collateral reports and records.

**Parent-Child Interaction Tasks**. Each Father-child dyad is video-taped in a semi-structured 20-minute play session. It consists of 15 minutes of free-play and a 5-minute clean-up. Each play session will be coded using the Child Interactive Behavior Coding which has been validated with children aged birth to 13 years. Infant, Preschool or Child coding guidelines will be used depending on child age. The following codes are used across ages: 1) parental hostility/intrusiveness, 2) dyadic reciprocity, and 3) child's relationship behavior toward the parent (avoidance, anxiety). Parents and children will be rated by trained blind coders who have attained .75 reliability to the task author [name]; 15% of the tapes will be double coded for reliability checks. The video recording of play assessments with the child pre and post treatment is necessary for coding father-child interactions before and after the treatment.

Child Mental Health. Symptom dimensions will be derived from father and mother reports on surveys with established reliability, validity, and developmental sensitivity. For data reduction purposes, continuous latent constructs will be identified via measurement models and secondorder factor models conducted in Mplus using standard fit criteria. If necessary, we will use other methods to reduce these data, e.g., latent constructs formed by principal components analysis. The TSCYC and TSCC includes 8 subscales assessing trauma symptoms and more common childhood symptoms and are used for children aged 3 to 17. For infants and toddlers, we will have parents complete the Brief Infant Toddler Social Emotional Assessment (ITSEA) Stratified Randomization. To increase the likelihood treatment groups are balanced on important variables (i.e., , residence with target child, protective order with coparent, substance use) participants will be assigned to treatment through stratified randomization. Following randomization, fathers will be assigned to either 18 sessions (once per week) of Fathers for Change or18 sessions of Duluth Batterer Intervention delivered in an individual format. We anticipate 140 participants in each treatment group. Research assistants managing the data [name] will be blind to treatment condition assignment during analysis. Participants will be recorded as receiving either "treatment 1", or "treatment 2". The research assistants and [name] will not be aware which treatment protocol "treatment 1" or "treatment 2" correspond to until analyses are complete.

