# Aims for Phase II:

AIM 1. Compare F4C to a standard BIP in its efficacy to reduce FV by decreasing fathers' violent behavior, improve father-child interactions, and reduce child mental health symptoms. *Hypotheses.* Children of fathers who receive F4C (n=140), relative to BIP (n=140), will: (1a) experience less FV, (1b) have more positive father-child interactions, and (1c) have lower FV-related mental health symptoms (PTSD, internalizing/externalizing) at post treatment and 6- and 12-month follow-ups. The effects of both treatments on father and coparent mental health outcomes will also be examined (1d *exploratory*).

AIM 2. Identify and compare latent change profiles of therapeutic targets (RF, ER) in F4C and BIP fathers across the 18-week intervention. *Hypotheses*. Compared to BIP, more F4C fathers will show profiles of healthy change in therapeutic targets: (2a) masked coding of insession RF/ ER (i.e., increased RF and adaptive ER, decreased maladaptive ER), and (2b)

between-session self-reported RF/ ER (i.e., increased RF and adaptive ER, decreased maladaptive ER). F4C change profiles will reveal critical junctures in treatment that precipitate change, thereby serving to optimize timing/delivery of treatment components (2c, *exploratory*).

AIM 3. Examine the mediating role of therapeutic change targets (RF, ER) on child-related outcomes in F4C and BIP families. *Hypotheses*. Profiles of healthy change in RF and ER will mediate the treatment effect of F4C over BIP on: (3a) FV (3b) father-child interactions, and (3c) child mental health symptoms (PTSD, internalizing/externalizing) at post-treatment and at 6- and 12-month follow-ups.

2. **Background:** Describe the background information that led to the plan for this project. **Provide references** to support the expectation of obtaining useful scientific data.

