What Intervention Mechanisms Could Reduce IPV and CM? Current Batterer Interventions target beliefs about the roles of women and power and control behaviors with limited impact on IPV. Recent research indicates BIPs that more carefully consider psychopathology and psychiatric needs or incorporate mindfulness and psychological flexibility instead of power and control may be more effective in reducing IPV. RF describes the capacity of individuals to understand their own and others' actions as a function of underlying psychological and emotional states and motivations. Individuals with high levels of RF are better able to recognize their own and others' thoughts, emotions, intentions, and desires. Poor RF is associated with increased violent and aggressive behavior and emotional dysregulation. Studies by the PI have indicated fathers with histories of IPV have very low levels of RF. Studies in mothers indicate a significant association between poor RF related to their children and maltreatment. While there is less research on the relationship between paternal RF and child maltreatment, poor RF is a potential core element driving male perpetrated IPV Reading of the larger literature suggests a common and potentially modifiable pathway to IPV and CM through RF. Men at risk for IPV/CM often misperceive threat (acute threat sensitivity) especially from their partners 48 and instead respond to innocuous or ambiguous stimuli with hostility and emotion dysregulation and violence. Lack of RF is important to this chain. Poor RF can result in: 1) misperceptions of partners and children's' intentions or behaviors and 2) lack of understanding of one's own emotions, triggers, thoughts, and behaviors and 3) poor regulation of emotion that can result in violence. The PI has demonstrated low RF in fathers with histories of IPV and experimental studies have indicated that improving emotion regulation reduces violence. Therefore, intervention like F4C that can increase RF could reduce IPV and child maltreatment.

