# Treatment Phase.

Each treatment will be delivered weekly over 18 weeks. Male participants will meet online or be contacted via phone weekly with the RA to complete self-report assessments of IPV behaviors, father-child interactions and *substance use*. The RAs will be blind to the participants' treatment conditions. Study therapists will complete weekly session reports of session content and skill acquisitions based on completed homework.

*Fathers for Change*: F4C focuses on: 1) the fathering role to facilitate engagement, 2) RF to understand self, partner and children and emotion regulation skills to reduce IPV and child maltreatment F4C focuses on understanding of emotional experiences, how they impact thinking and behaviors related to partners, co-parents and children. F4C clients will meet individually with their F4C therapist for 50 minutes per week over 18 weeks.

**Batterer Intervention Program:** The BIP is a psychoeducational intervention that will be delivered in 50- minute individual sessions over 18 weeks. The intervention focuses on the impact of violence on victims, power and control tactics, and societal influences supporting men's violence toward women. The intervention includes didactics and experiential exercises including role plays to teach management skills. anger BIP is typically delivered in a group format, however will also be adapted to an individual Therapies will be delivered either in person or via format as part of the current study. secure/password protected zoom virtual sessions. All Yale safety protocols with regard to COVID-19 will be followed.

**Therapist Training.** Master's level clinicians will be trained to deliver the study interventions. [name] will utilize the therapist training manual, slides and videos generated from her pilot studies to train F4C therapists. She will meet weekly with F4C therapists for supervision. BIP-I and BIP-G therapists will be trained by [name] using the BIP manual and training materials modified for individual treatment delivery. BIP clinicians will meet weekly with [name] for supervision and intervention adherence.

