**Exclusion Criteria**. Men will be excluded who have: 1) an active full/no contact protective order pertaining to their child since this will preclude participation in the father-child play assessment (many men will have full no-contact orders with their partners, but it is more common for men to still be allowed at least supervised contact with their children even with a full/no contact order with their partner); 2) physiological addiction to a substance that requires detoxification. Fathers will be evaluated using the AUDIT and DAST. If fathers report difficulties with physiological withdrawal from substances (e.g. delirium tremens, shaking, nausea) they will be referred for detox services. They can be re-evaluated following a detox program with documentation from the detox center of successful completion and clean urine screen.; 3) cognitive impairment that will not allow for understanding of the study interventions (a mini mental state score <25); 4) current untreated psychotic disorder; 5) currently suicidal or homicidal based on screening using the BSI; 6) Are currently enrolled or have previously received F4C or BIP; 7)coparent declines to provide collateral information about their child's symptoms.

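### Child-symptom outcomes for 1c and 3c draw on father and mother reports without separating them, so an arm-specific shift in the treated father's reporting could move the result with no change in the child

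*Combined protocol and SAP*

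**What the plan says.** Hypothesis 1c (Section IV.1, Aims for Phase II) is that children of F4C fathers will "have lower FV-related mental health symptoms (PTSD, internalizing/externalizing) at post treatment and 6- and 12-month follow-ups". Hypothesis 3c takes the same symptoms as the outcome of a mediation analysis.

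The outcome is defined in Section IV.3, Child Mental Health: "Symptom dimensions will be derived from father and mother reports on surveys with established reliability, validity, and developmental sensitivity". For data reduction, "continuous latent constructs will be identified via measurement models and secondorder factor models conducted in Mplus", and if necessary other methods, such as "latent constructs formed by principal components analysis". Table 1 names mother and father as raters of the symptom checklists and of the PTSD interview modules. Older children also self-report on the checklist. Section VII.2, Protection of Child Participants, gives that self-report a corroborating role, and no analysis of it is stated.

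Masking is described for research assistants, coders and analysts. None is described for fathers.

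The Treatment Phase text says that F4C works on "RF to understand self, partner and children and emotion regulation skills to reduce IPV and child maltreatment". The Background (Section IV.2) lists, among the results of poor reflective functioning (RF), "misperceptions of partners and children's' intentions or behaviors". BIP is described as covering the effect of violence on victims, power and control, and societal influences.

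The plan states no analysis by informant, no informant or method factor, no test of measurement invariance by arm and time, and no single-informant sensitivity analysis.

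**The concern.** One of the two symptom reporters receives the randomised treatment, and by the protocol's own theory F4C changes how he perceives the child. A father with better RF might notice distress that he used to miss, and report more symptoms. He might instead read less hostility into the child's behaviour, and report fewer. Either change would move his items together. Unless the model separates informants, it can pass into the symptom dimension as if the child had changed.

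BIP has a different focus, so the shift need not cancel between arms. It could hide a real benefit on 1c or create an apparent one.

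3c is more exposed. Its mediator includes the father's self-reported RF and emotion regulation (ER), and part of its outcome comes from the same father, so variance shared within one rater could look like mediation.

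Some reports may also rest on little observation. The inclusion criteria accept monthly contact, which may be by phone.

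**Working it through.** **The plan's own figure.** The Aim 1 power statement (Phase II Hypotheses) gives power .91 for d = 0.12 with 140 per arm. A two-sample normal approximation at two-sided alpha 0.05 (assumed, as none is stated) has noncentrality 0.12 × √(140/2) = 1.00 and power of about 0.17, so it does not reproduce .91. A repeated-measures group-by-time test with f = 0.06 gives 0.82 and 0.945 (three waves), or 0.88 and 0.975 (four waves), at within-person correlations of 0.7 and 0.8. So .91 is reachable only with a correlation that the plan does not state. The present point does not depend on this figure. I use d = 0.12 only as the plan's own yardstick.

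**Inputs for the illustration**
- From the plan: 140 per arm, and 98 per arm after 30% loss (140 × 0.70 = 98, consistent with the 196 complete cases in Section V: 196/2 = 98).
- Assumed: no true effect on the child; a between-arm shift of b SD in father report only; father-mother correlation r; an equal-weight mean of the two standardised reports. Neither b nor r is in the documents, and the planned factor weights are unspecified.

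**Shift in the composite.** The mean moves by 0.5b and has SD √((1 + r)/2), so

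d = 0.5b / √((1 + r)/2).

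For b = 0.2 and r = 0.3: d = 0.10 / √0.65 = 0.124.

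Solving for b at d = 0.12: b = 0.24 × √((1 + r)/2), which is 0.19 at r = 0.2 and 0.21 at r = 0.6.

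**Chance of a false finding in either direction** (two-sided z-test at 0.05, standard error √(2/n)):

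| b | r | composite d | n = 140 | n = 98 |
|---|---|---|---|---|
| 0.1 | 0.6 | 0.056 | 7.5% | 6.8% |
| 0.2 | 0.3 | 0.124 | 18% | 14% |
| 0.3 | 0.3 | 0.186 | 34% | 26% |
| 0.5 | 0.2 | 0.323 | 77% | 62% |

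The first and last rows are the extremes over b = 0.1 to 0.5 and r = 0.2 to 0.6.

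**Cost of one informant.** If the true effect were d = 0.3 in each report (assumed), coparent report alone has power 0.71 against 0.80 to 0.90 for the composite at 140 per arm, and 0.56 against 0.65 to 0.77 at 98.

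**What an intercept test can show.** The father-minus-mother difference has SD √(2(1 − r)). For b = 0.2 and r = 0.3 the arm contrast is 0.2 / √1.4 = 0.169 SD. Power is about 0.29 at 140 per arm (0.169 × √70 = 1.41) and 0.22 at 98 (0.169 × 7 = 1.18). A non-significant result would therefore not rule out a shift large enough to matter.

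**The case against.** The strongest reply is that the model is not fully written down. The text speaks of dimensions and constructs in the plural and of second-order factors. A reader might infer that all father and mother items are merged into a single score. The documents do not say so, and a second-order structure could hold father and mother first-order factors, leaving some father-specific variance out of the common factor. That stands. The defect is that the separation is unspecified, and a principal-components fallback across informants would not provide it.

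A reader might also infer that coparent report is a ready, clean replacement. The documents do not support this, for three reasons.
- Exclusion 7 removes a father whose coparent "declines to provide collateral information about their child's symptoms", but Section VII.2, Additional Safety and Comfort, lets a man remain when his partner declines participation for herself. Her report may therefore not exist for every family. Exclusion 7 is also an entry criterion, while 1c is tested after treatment and at 6 and 12 months, with 30% attrition assumed.
- F4C includes four co-parent topics (Section IV.2), and coparent mental health is itself examined in 1d, so her reporting may also shift by arm.
- Using her report alone gives up the precision shown above.

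A further tempting reading is that fathers will report improvement in order to show success, which would favour F4C. Fathers in both arms are referred because of IPV or maltreatment risk, and either treatment may serve as mandated treatment (Section VI.1). That motive is therefore not specific to one arm. Only the RF mechanism differs by design, and its direction is unknown.

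Finally, the named primary measure is the FSI-R, rated by masked coders, and not child symptoms. That limits the scope to 1c and 3c.

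**Conclusion.** The concern holds in this form: the plan lets the treated father's reports enter the 1c and 3c symptom dimensions with nothing specified to separate a change in his reporting from a change in the child. That he is unmasked is inferred from the therapy format and the absence of any masking statement for fathers. That the shift could differ by arm follows from the protocol's own account of what F4C targets.

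Neither the size nor the direction is known. Under the assumed equal weights, a father-only shift of about 0.2 SD is enough to produce d = 0.12. The documents do not show that such a shift will occur, that it would favour F4C, or that coparent report is free of bias. The matter should be settled before the analysis. It does not touch the FSI-R as the named primary measure.

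**What to change.** In Section IV.3, Child Mental Health, and the Aim 1 and Aim 3 analysis text:

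1. Specify a two-informant model with separate father and mother method factors. Test whether father-report intercepts differ by arm after treatment, and report the difference with a confidence interval. With two informants this contrast takes the mother's reporting as the reference, so state that assumption. Do not treat a non-significant test as clearance.
2. Drop principal components across informants. If that fallback is needed, apply it within informant.
3. Prespecify the 1c and 3c arm effects separately by coparent report and by father report, with child self-report (age 7 and up) as supportive. Do not claim 1c or 3c if the effect appears only in father report.
4. Reconcile exclusion 7 with Section VII.2 on whether a father may take part without coparent symptom data, and state how missing coparent reports are handled.

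This uses data already planned and needs only plan wording and somewhat more analysis. The costs are lower precision for the single-informant results, missing coparent reports at follow-up, and a coparent who may herself be exposed to F4C content.

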# Treatment Phase.

Each treatment will be delivered weekly over 18 weeks. Male participants will meet online or be contacted via phone weekly with the RA to complete self-report assessments of IPV behaviors, father-child interactions and *substance use*. The RAs will be blind to the participants' treatment conditions. Study therapists will complete weekly session reports of session content and skill acquisitions based on completed homework.

*Fathers for Change*: F4C focuses on: 1) the fathering role to facilitate engagement, 2) RF to understand self, partner and children and emotion regulation skills to reduce IPV and child maltreatment F4C focuses on understanding of emotional experiences, how they impact thinking and behaviors related to partners, co-parents and children. F4C clients will meet individually with their F4C therapist for 50 minutes per week over 18 weeks.

**Batterer Intervention Program:** The BIP is a psychoeducational intervention that will be delivered in 50- minute individual sessions over 18 weeks. The intervention focuses on the impact of violence on victims, power and control tactics, and societal influences supporting men's violence toward women. The intervention includes didactics and experiential exercises including role plays to teach management skills. anger BIP is typically delivered in a group format, however will also be adapted to an individual Therapies will be delivered either in person or via format as part of the current study. secure/password protected zoom virtual sessions. All Yale safety protocols with regard to COVID-19 will be followed.

**Therapist Training.** Master's level clinicians will be trained to deliver the study interventions. [name] will utilize the therapist training manual, slides and videos generated from her pilot studies to train F4C therapists. She will meet weekly with F4C therapists for supervision. BIP-I and BIP-G therapists will be trained by [name] using the BIP manual and training materials modified for individual treatment delivery. BIP clinicians will meet weekly with [name] for supervision and intervention adherence.

**Treatment Fidelity.** Each intervention session will be video recorded. Trained coders will rate 20% of sessions for fidelity and change in emotion regulation/reflective functioning during therapy sessions using the F4C/BIP Fidelity Measure and the CHANGE coding system. Tape raters for fidelity will be trained by the PI coding a set of 6 practice tapes. Fidelity feedback will be provided by Drs. [name] (F4C) and [name] (BIP) in their respective supervision sessions with study therapists to ensure fidelity and allow corrective feedback. Tape raters will be trained by [name] for the CHANGE session coding system and will be supervised by [name] at the University of Delaware and [name] at the University of Connecticut. The Change and Growth Experiences Scale (CHANGE; Hayes, Feldman, & Goldfried, 2007) is an observational coding system that assesses processes of change during psychotherapy, including factors that facilitate and inhibit therapeutic change. The CHANGE has been used to code audio and video recordings of sessions or narratives from clinical trials of trauma-focused cognitive behavioral therapy (TF-CBT) for youth (Alpert et al., 2021; Canale et al., 2021; Ready et al., 2015; Yasinski et al., 2016), prolonged exposure, written exposure therapy (WET), and cognitive processing therapy (CPT) for adult PTSD (Alpert, 2021; Alpert et al., 2020; Sloan et al., 2021), as well as cognitive-behavioral treatments for depression (Abel et al., 2016; Adler et al., 2013; Hayes, Feldman, Beevers et al., 2007; Yasinski et al., 2020) and personality disorders (Hayes & Yasinski, 2015). The CHANGE has been used to identify key predictors of treatment dropout and outcomes in each of these clinical trials.

# Weekly and Monthly Measures During Treatment

The RA will meet with fathers via password protected zoom link or in person to complete logs of IPV, substance use and interactions with their children and monthly assessments of working alliance and treatment motivation via computerized survey at the time of their weekly clinical appointment. If fathers do not show for their appointment RAs will phone him to collect the information or email a secure survey. All data will be entered into a secure web-based REDCap database.

**TimeLine Follow-back-Spousal Violence, Child Maltreatment Risk, & Substance Use (TLFB-SV/SU/CM)** will be used to assess specific types of IPV (physical, sexual, psychological) toward partners on any given day, contact with the target child and child maltreatment risk behaviors (yelling, swearing, spanking, slapping, ignoring, harsh punishment). The TLFB-SV/SU/CM will be administered weekly to assess violence, substance use and CM risk behaviors during treatment. This is a reliable and valid instrument that has been used to assess relationship violence over time and links to substance use.  Participants, *the mother of their youngest child and if different their current female partner* will be asked to report IPV and CM throughout treatment.

**Measures of Treatment Targets:** Fathers will complete items from the Parental Acceptance Rejection Questionnaire, COPES and Unified Protocol Skill Use Scale to assess intervention coping skill use and emotion regulation/RF changes during treatment.

**Measures of Treatment Process:** Fathers will complete the **Working Alliance Inventory**,  **Motivation to Change** (85) on a monthly basis and the **Client Satisfaction Questionnaire** at the end of treatment to document (a) the quality of their relationship with their clinician, (b) their perceived motivation for change, and (c) satisfaction with treatment.

